5.4 Dose limiting toxicity and subsequent courses at reduced dose

5.4.1 Definition of DLT

The definition of DLT in this study differs from the standard definition. Dose-limiting toxicity (DLT) will be defined as Grade 3 or 4 toxicity, using the NCI Common Terminology Criteria for Adverse Events (CTCAE), version 3.0, EXCEPT as detailed below in Section 5.4.3. These toxicities will be evaluated for all subjects beginning on Course 1 day 1 during all courses of this study except for the time from the initiation of the surgical resection until recovery from surgery and initiation of Course 1 (for Group B) or Course 2 (for Group A) of protocol treatment.

5.4.2 Clarification of need for exceptions for DLT determination

Since a secondary objective of this study is to evaluate adverse events associated with this experimental agent, careful documentation of toxicity (according to the NCI CTCAE version 3.0) is essential. Though the hu14.18-IL2 fusion protein is a relatively new molecule with modest clinical testing, it is derived from the human IL2 molecule and the humanized form of the ch14.18 chimeric antibody, both of which have had extensive clinical testing. Over the past 15 years of IL2 testing and 9 years of ch14.18 testing, certain side effects have been noted to occur frequently. These toxicities are generally transient, can be well controlled clinically and/or resolve spontaneously, and have no sequelae. Therefore, though some of these frequently seen side effects do score as Grade 3 or 4 toxicities, using the NCI CTCAE 3.0 scale, these toxicities have been excluded for determination of “dose-limiting toxicity” for both IL2 or ch14.18. The list of frequently seen toxicities below will therefore not be considered as dose limiting for the purposes of drug discontinuation, dose modification, or DLT determination for this study.

In order to evaluate the clinical anti-tumor activity and duration of response of hu14.18-IL2 in subjects with advanced melanoma, subjects enrolled in this clinical study will be treated at

6mg/M²/d, a dose below the MTD, as determined in our adult Phase I clinical trial and at a dose well tolerated (without DLT) in our recently completed Phase II trial.

5.4.3 Detailed listing of DLT exceptions

The following toxicities will be graded and recorded, but will not be used as criteria for determining DLT:

- a) Grade 3 pain, requiring intravenous narcotics, provided that the narcotics are controlling the pain, and that IV narcotics for pain are not required > 48 hours after completion of hu14.18-IL2 on Day 3 of any treatment course;
- b) Grade 3 nausea and vomiting that resolves within 48 hours after completion of hu14.18-IL2 on Day 3 of any treatment course;
- c) Grade 3 fever (i.e., T > 40° C) lasting < 6 hours and controllable with antipyretics;
- d) Grade 3 skin toxicity that improves with treatment (e.g., IV Benadryl) within 24 hrs;
- e) Grade 3 metabolic/laboratory toxicity of hyponatremia, hyperglycemia, or hypophosphatemia in the absence of CNS symptoms and/or sequelae, that improves with or without treatment within 48 hrs;
- f) Grade 3 sensory or motor peripheral (non-cranial) neuropathy (i.e., interference with function plus objective weakness) if transient and reversing within 3 days of completion of hu14.18-IL2 of any treatment course. Subjective findings (e.g., tingling, hot/cold hands) are expected and will not be DLT;
- g) Grade 3 hematologic toxicity (or grade 4 lymphopenia – a known transient marker of immune activation by IL2) which improves to at least Grade 2 or pre-therapy baseline values without requiring transfusion within one week of completion of hu14.18-IL2 of any treatment course (see Section 10.2.1 for management of hematologic toxicity and transfusion guidelines);
- h) Grade 3 infusional reactions lasting less than 24 hours, readily controlled with supportive (non-steroidal) treatments (i.e., Benadryl) and not requiring epinephrine;
- i) Grade 3 fatigue or ECOG performance status that resolves in ≤ 1 week;
- j) Grade 3 infection that resolves in ≤ 1 week.

The above dose limiting toxicity exceptions are based on the known, published, transient, reversible toxicities of IL2 and hu14.18. These toxicities may be expected, based on observations of hu14.18-IL2 given to 33 + 14 (phase I and II respectively) adults with melanoma, administered by the same schedule at similar doses to that being tested in this trial, and will not require interruption, modification, or discontinuation of treatment. In our experience with hu14.18-IL2 in adults with melanoma, asymptomatic hypophosphatemia is a relatively frequent occurrence. Therefore, all subjects scheduled to receive this agent will be given oral phosphate supplementation prophylactically starting on day 1 and ending on day 8 of each course (see Section 10.3.4.3 for details). **All grade 4 toxicities (except for transient lymphopenia) are considered as DLT and require stopping treatment with hu14.18-IL2. Following resolution of a DLT, and if subsequent hu14.18-IL2 treatment is given, it must be given at a reduced dose.**

5.4.4 Treatment cessation/dose modification for DLT or significant non-DLT toxicity

Any subject demonstrating DLT or significant non-DLT toxicity (see Section 10.1.2) will require that treatment with the study agents be stopped. Depending upon the nature of the toxicity and its resolution, subjects will be considered for continued treatment at a reduced dose as described below (see also Figure 1). Any planned drug administration that is withheld due to DLT will not be given on a delayed schedule to “make up” for missed drug. All dose modifications are permanent.

5.4.4.1 Dose-reduction plan for hu14.18-IL2

For toxicity associated with hu14.18-IL2, there must also be consideration of the schedule of administration. If this toxicity occurs on day 1 or 2 of any course, treatment can be resumed during that same course (i.e., on day 2 or 3) at 50% of the starting dose only if the toxicity has improved to meet eligibility criteria in time to give the day 2 or day 3 dose on schedule. If eligibility criteria are not met in time to receive additional therapy during the course in which the toxicity occurred, but are met in time to start the next course (i.e., day 1 of the next course +/- 7 days), treatment will resume at 50% of the dose that caused the DLT. If toxicity again requires treatment cessation, treatment can be restarted at 25% of initial treatment dose. If treatment at this reduced dose results in recurrence of DLT or significant non-DLT toxicity, treatment will be permanently discontinued.

Repeat lab testing will be done weekly until eligibility criteria are met, and treatment will begin at 50% of the prior dose. If after 4 additional weeks of testing, eligibility criteria still are not met, the subject will not be eligible for any additional treatment with the study agent responsible.

Subjects with Grade 4 toxicity related to protocol treatment (other than transient lymphopenia from hu14.18-IL2, see Section 5.3.3.g) will not receive additional protocol treatment during that treatment course. Patients experiencing Grade 4 neutropenia or leukopenia that lasts \leq 4 days; Grade 4 thrombocytopenia that can be corrected with platelet transfusion (see Section 10.2.1); or Grade 4 nausea, vomiting, anorexia or fatigue lasting less than 2 days, and resolves to meet eligibility criteria, may be eligible to receive continued study therapy (provided that all other criteria for continued treatment are met) at 50% of the dose received prior to the onset of this toxicity. Subjects with any other Grade 4 toxicity related to the protocol treatment will not receive additional protocol treatment during that course and will be withdrawn from the study. Subjects experiencing Grade 4 events that are clearly unrelated to the study treatment, last \leq 3 days, and improve to meet eligibility criteria, may be eligible to receive continued study therapy (provided that all other criteria for continued treatment are met) at 50% of the daily dose received prior to the onset of this toxicity.

[figure not shown]

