10.1.1 Dose modification for DLT

Dose limiting Toxicity (DLT) criteria and exclusions are described in protocol section 5.3. For any occurrence of DLT, treatment with protocol therapy will be stopped. Treatment may not be resumed until after toxicity has resolved to meet original eligibility criteria. Resuming treatment following any DLT at a reduced dose (according to the guidelines below) requires contact (by phone or e-mail) with the FDA on a case-by-case basis. The first contact will be to the FDA Oncology Drug Products review division in the Center for Drug Evaluation and Research at [contact]. An alternate contact is at the following: [contact]; [contact], [contact].

For toxicities occurring during treatment with hu14.18-IL2, if DLT occurs on day 1 or 2 of any course, treatment can only be resumed during that same course (i.e., on day 2 or 3) at 50% of the starting dose, and only if the toxicity has resolved to meet eligibility criteria in time to give the day 2 or day 3 dose on schedule. If eligibility criteria are not met in time to receive additional therapy during the course in which the toxicity occurred, but are met in time to start the next course (i.e., day 1 +/- 7 days), treatment will resume at 50% of the dose associated with the DLT. Any planned drug administration that is withheld due to DLT will not be given on a delayed schedule to “make up” for missed drug. If toxicity again requires treatment cessation, treatment can be restarted at 25% of initial treatment dose. If treatment at this reduced dose results in recurrence of DLT or significant non-DLT toxicity, treatment will be permanently discontinued. Treatment will be resumed, as described above, using only 50% of the starting dose of hu14.18-IL2, and only if the toxicity has resolved to meet eligibility criteria.

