10.1.2 Dose modification for toxicity that is not graded as DLT

It is the intention of this pilot study to treat all patients, at all courses, at the starting doses of 6 mg/m²/d for hu14.18-IL2, or the maximum dose that each patient demonstrates is tolerable for them. However, if severe toxicity is observed, such that the investigator feels discontinuation of treatment at the dose level causing the toxicity is in the patient’s best interest, temporary or permanent cessation of treatment at that dose level, or a 50% dose reduction for subsequent infusions (in the absence of DLT) is permissible. Justification for discontinuation of therapy or dose reduction must be clearly documented. At no time will the dose level be escalated.

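### A subject already halved to 3 mg/m²/d without a DLT would, on the literal same-course rule, resume at that same 3 mg/m²/d after a first DLT

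*Combined protocol and SAP*

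**What the plan says.** All subjects start at 6 mg/m²/d on days 1 to 3 of each course. The dose can fall before any DLT has occurred: under 10.1.2, for severe toxicity that is not graded as DLT, "a 50% dose reduction for subsequent infusions (in the absence of DLT) is permissible". Section 5.4.4 adds "All dose modifications are permanent", and 10.1.2 rules out escalation.

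After a DLT, the resumption dose depends on when the subject recovers.

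- **Recovery within the course.** For toxicity on day 1 or 2, 5.4.4.1 says "treatment can be resumed during that same course (i.e., on day 2 or 3) at 50% of the starting dose". Section 10.1.1 repeats the rule: "treatment can only be resumed during that same course (i.e., on day 2 or 3) at 50% of the starting dose".
- **Recovery by the next course.** In 5.4.4.1, "treatment will resume at 50% of the dose that caused the DLT". Section 10.1.1 matches it.
- **Later recovery.** Section 5.4.4.1 retests weekly and restarts at half the prior dose.
- **Repeat toxicity.** "If toxicity again requires treatment cessation, treatment can be restarted at 25% of initial treatment dose" (5.4.4.1). Toxicity at that level ends treatment, and 5.5.1(b) removes a subject with a DLT at 25% of the starting dose.

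Over all of these stands 5.4.3: "Following resolution of a DLT, and if subsequent hu14.18-IL2 treatment is given, it must be given at a reduced dose". Section 5.4.4 also brings non-DLT events into the scheme: "Any subject demonstrating DLT or significant non-DLT toxicity (see Section 10.1.2) will require that treatment with the study agents be stopped".

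**The concern.** The same-course rule takes its 50% from the starting dose, not from the dose the subject was receiving. For a subject still at 6 mg/m²/d the two are the same. For a subject already halved under 10.1.2 they are not: half of the starting dose is the current dose. Followed to the letter, the clause re-treats the subject within one or two days at the dose that has just caused a DLT, and 5.4.3 forbids that. Section 5.4.3 requires a reduction but gives no figure, so whoever writes the order for the next infusion has a number that breaks the rule and a rule that has no number.

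**Working it through.** No sample-size or power figure is involved. The check applies each resumption rule to two subjects, one at full dose and one already halved.

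**Inputs.** Starting dose 6 mg/m²/d (5.3, 10.1.2). Dose after a non-DLT halving: 0.50 × 6 = 3 mg/m²/d (10.1.2), permanent (5.4.4). Three infusions per course (5.3). Infusions withheld for DLT are not made up (5.4.4).

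| Rule | When it applies | Formula | Subject at 6 | Subject at 3 |
|---|---|---|---|---|
| Same course (5.4.4.1, 10.1.1) | DLT on day 1 or 2, recovered for day 2 or 3 | 0.50 × 6 | 3.0 | **3.0** |
| Next course (5.4.4.1, 10.1.1) | recovered only for the next course | 0.50 × dose causing the DLT | 3.0 | 1.5 |
| Weekly retest (5.4.4.1) | recovered later still | 0.50 × prior dose | 3.0 | 1.5 |
| Repeat toxicity (5.4.4.1, 10.1.1) | toxicity forces a stop again | 0.25 × 6 | not yet reached | 1.5, if the earlier non-DLT event counts |

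**Against 5.4.3.** At full dose 3.0 < 6.0, so the same-course rule is a reduction. For the halved subject 3.0 is not below 3.0, so it is not.

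**Which DLTs.** Section 5.4.4.1 bars further dosing in the same course after related Grade 4 toxicity other than transient lymphopenia. The clause therefore matters for Grade 3 DLTs outside the exceptions in 5.4.3. Grade 3 vascular leak syndrome is the clearest example: 10.2.3.3 gives no restart dose of its own and refers to 10.1.

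**Size within the course.**
- DLT on day 1, two infusions left: 2 × 3.0 = 6.0 against 2 × 1.5 = 3.0 mg/m², a difference of 3.0.
- One infusion left (DLT on day 2, or on day 1 with recovery only by day 3): 3.0 against 1.5 mg/m², a difference of 1.5.
- If 3 mg/m²/d were also carried into a full later course: 3 × 3.0 = 9.0 against 3 × 1.5 = 4.5 mg/m².

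**How often.** The Overview reports no protocol-defined DLT in 14 Phase II patients at 6 mg/m²/d. The one-sided 95% upper limit is 1 − 0.05^(1/14) = 0.193, assuming a comparable DLT definition. That limit is for 6 mg/m²/d; the case here needs a DLT at 3. The nearest Phase I level is 3.2 mg/m² (Table 1), where 2 of 6 subjects had a DLT, both hyperglycemia with known diabetes. Diabetes that needed drug treatment in the past 3 months is now excluded (3.2.19), and Grade 3 hyperglycemia that improves within 48 hours without CNS symptoms or sequelae is exempt (5.4.3). The documents give no usable DLT rate at 3 mg/m²/d.

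**The case against.** The strongest reply is that the plan, read as a whole, already gives 1.5 mg/m²/d. Section 5.4.4 covers significant non-DLT toxicity and cites 10.1.2, and 5.4.4.1 opens with toxicity in general. A 10.1.2 halving is then the first step and the later DLT is repeat toxicity, which goes to 25%. This is a reasonable reading and probably the intended one. It remains an inference. Section 10.1.2 offers a reduction as an alternative to stopping, so a halved subject need not have had a first cessation for the DLT to repeat. Footnote 4 to the dose-reduction figure counts only DLTs. The same-course clause applies in any course and makes no exception.

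Other safeguards also stand. Section 5.4.3 demands a reduction, same-course resumption is optional, and 10.1.1 requires FDA contact case by case. Several toxicities have their own restart rules in 10.2: hypotension has 50% and 25% steps, recurrent dyspnea with low oxygen saturation restarts at half the prior dose, and fever, confusion and pain are each tied to the causing or prior dose. These shrink the affected group. They do not correct the number in the clause.

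A reader might infer that the next-course and weekly-retest clauses compete with the same-course clause. They do not, because they apply only when recovery comes later. What they show is the pattern the plan uses elsewhere. A reader might also cite footnote 4 and the closing sentence of 10.1.1 as further instructions to give 3 mg/m²/d. The figure is not shown and the closing sentence refers back to the text before it, so neither carries the point alone.

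**Conclusion.** The point holds as a minor safety-wording error. In one sequence (a 10.1.2 halving, then a first non-exempt Grade 3 DLT on day 1 or 2, then recovery to eligibility criteria before the next scheduled infusion) the same-course clause literally gives an unchanged 3 mg/m²/d, against 5.4.3. The size is 1.5 to 3.0 mg/m² of drug in that course. The 4.5 mg/m² difference per full course arises only if the unreduced dose is carried forward.

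Three stronger conclusions are not supported. The plan does not leave subjects with DLTs in general unprotected: at 6 mg/m²/d the rules agree on 3 mg/m²/d, and a second DLT is covered by the 25% rule. The 19% limit neither estimates nor bounds the risk at 3 mg/m²/d. No endpoint is affected. With a planned 16 to 20 subjects, the case may never arise.

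The conclusion rests on the literal text and on the figure, which could not be seen, not settling the case.

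**What to change.** 1. In the same-course clauses of 5.4.4.1 and 10.1.1, and in the closing sentence of 10.1.1, base the 50% on *the dose at which the DLT occurred* instead of the starting dose.
2. Add one sentence to 5.4.4.1 and 10.1.1: *Any earlier dose reduction, including one under 10.1.2, counts as a step on the 50% / 25% / stop ladder; treatment is not restarted after DLT or significant non-DLT toxicity at 25% of the starting dose.*
3. After checking against Figure 1, make all three lines of footnote 4 (first, second and third DLT) follow the same step count. Changing only the first line would leave the second giving 1.5 mg/m²/d again to a subject who reached 1.5 after a 10.1.2 cut and one DLT.

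The added sentence alone would settle the intent. The replacements are still needed so that the clause does not contradict it. The ladder becomes 6, 3, 1.5 mg/m²/d, then off therapy, in agreement with 5.5.1(b).

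The cost is a few lines of amendment and, for the rare affected subject, 1.5 to 3.0 mg/m² less drug in that course. A subject at 6 mg/m²/d still resumes at 0.50 × 6 = 3 mg/m²/d.

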5.5.1 Criteria for removal from protocol therapy

- a) Progressive disease. Subjects with symptomatic disease recurrence confirmed clinically or radiologically at any time will be removed from protocol therapy. Subjects showing asymptomatic disease recurrence at any of the scheduled clinical monitoring times will be removed from protocol therapy. See Section 6.0 for criteria for recurrent disease.
- b) Drug intolerance (i.e., subjects who experience DLT) at 25% of the starting dose.
- c) Treatment-related toxicities that have not recovered to \leq Grade 2 in 2 weeks following day 3 of any treatment course of hu14.18-IL2.
- d) Refusal of further protocol therapy by subject.
- e) Completion of the 3 allowable courses of therapy.
- f) Physician determines that removal from protocol therapy is in subject's best interest.

Subjects who are off protocol therapy are to be followed until they meet the criteria for Off Study (see Section 5.5.2). Follow-up data will be required unless consent was withdrawn.

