5.5.2 Off study criteria

- a) Death.
- b) Lost to follow-up.
- c) Withdrawal of consent for any further data submission.

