6.6 Management of recurrence

Once recurrent disease is identified (and preferably confirmed histologically or cytologically), the responsible physician should initiate whatever treatment is indicated clinically. Subject survival data will still be collected, as will clinical evaluations for potential long-term toxicity.

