7.6 Late evaluation for recurrence or late toxicity

The following schedule (Table 8) describes clinical evaluations, lab testing and immunological samplings suggested for subjects following completion of all study treatment, to be evaluating for late effects of the treatment as well as time to recurrence. The exact tests to be ordered will be left to the discretion of the treating physician(s) as they feel appropriate, given each subject’s clinical history and presenting symptoms and signs. Subjects who have recurrence of disease will be followed for survival only.

TABLE 8.
CLINICAL ASSESSMENT GUIDELINES FOR RECURRENCE OR LATE TOXICITY

	2 & 4 months after treatment completion of cycle 3 therapy (months 5 & 7)	Every 3 months (months 10-25)	Every 6 months (starting at month 31)	At time of recurrence¹
Interim complete history and Physical Exam	X	X	X	X
Adverse event assessment	X	X	X	X
Weight	X	X	X	X
Performance Status	X	X	X	X
Tumor Assessment	X²	X²	X²	X^{2,3}
Vital signs (T, BP, P, RR)	X	X	X	X
CBC, diff, plts ⁴	X	X	X	X
AST, ALT, T bili, alk phos, alb, LDH, Na, K, Cl, HCO ₃ ,Cr, BUN, Glucose, Ca, Mg, Phosphate ⁴	X	X	X	X
INR/PTT ⁴	X			X
Urinalysis ⁴	X			X
Biopsy				X⁵

¹ These evaluations will be performed only at the time that disease recurrence is noted. Following this time, subjects will be followed only for survival.

² These evaluations should include CT scans of all areas of known prior metastatic disease. Other examinations can be performed as warranted clinically. If, at any of these evaluations, a potential for recurrent disease is identified, appropriate clinical studies (additional X-rays, scans, and/or lab tests, as clinically indicated) will be performed to identify and localize potential recurrent disease.

³ If recurrent disease is identified clinically or radiologically, efforts should be made to confirm its neoplastic nature by biopsy.

⁴ The exact laboratory tests to be obtained at follow-up visits shall be left to the discretion of the treating physician(s) as they are indicated clinically.

⁵ Recurrence should be confirmed by biopsy whenever possible. If possible and clinically indicated, the biopsy should be a core or excisional biopsy performed at the UWCCC. In doing so, fixed and fresh tissue can be evaluated with the same techniques used to evaluate the surgically resected tissue from this same subject as part of this study.

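### Section 5.4.4.1 withdraws subjects with non-exempt related Grade 4 toxicity from the study, contradicting 5.5.1 and 5.5.2; applied literally, it could end follow-up because of toxicity

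*Combined protocol and SAP*

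**What the plan says.** **Grade 4 rule (5.4.4.1).** The section handles related Grade 4 toxicity in three tiers.
- One event is carved out: "other than transient lymphopenia from hu14.18-IL2".
- Subjects with certain brief or correctable events "may be eligible to receive continued study therapy (provided that all other criteria for continued treatment are met) at 50% of the dose received" before onset. These events are neutropenia or leukopenia of at most 4 days, thrombocytopenia corrected by platelet transfusion, and nausea, vomiting, anorexia or fatigue of under 2 days.
- Subjects with any other related Grade 4 toxicity "will not receive additional protocol treatment during that course and will be withdrawn from the study".

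**Follow-up rule (5.5.1, 5.5.2).** Section 5.5.1 ends with the instruction "Subjects who are off protocol therapy are to be followed until they meet the criteria for Off Study", and withdrawn consent is the only exception it gives to collecting follow-up data. Section 5.5.2 has three Off Study criteria: death, loss to follow-up, and "Withdrawal of consent for any further data submission".

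**Endpoints (9.2.1).** Overall survival runs from randomization. Time to recurrence runs from the evaluation after course 2. Subjects without an event are censored at their last available evaluation.

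**After recurrence.** Section 6.6 says "Subject survival data will still be collected, as will clinical evaluations for potential long-term toxicity". Section 7.6 says "Subjects who have recurrence of disease will be followed for survival only", and Table 8 footnote 1 repeats the restriction.

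**The concern.** The protocol defines two exits: stopping treatment, after which data collection continues, and leaving the study, after which it does not. Section 5.4.4.1 sends a toxicity event to the second exit, although 5.5.2 does not recognise toxicity as a reason for it. A site cannot follow 5.4.4.1 to the letter and also comply with 5.5.1.

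Time to recurrence and overall survival are primary endpoints, summarised by Kaplan-Meier medians and two-year rates. Those methods assume that censoring is unrelated to outcome. Censoring triggered by severe drug toxicity is hard to defend on that ground: the subject has received less drug, and toxicity may go with immune activation or with prognosis. Objective 2.2.1 also seeks late adverse effects in subjects who remain in remission, and subjects with severe acute toxicity are ones in whom that information matters.

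**Working it through.** **1. Is the difference in wording only shorthand?** The other toxicity exits use the treatment term:
- 10.2.3.2.2 (recurrent hypotension at the 25% dose): off protocol therapy.
- 10.2.3.4 (recurrent dyspnea with desaturation at the 25% dose): off protocol therapy.
- 10.3.3.5 (corticosteroid use): withdrawal from protocol therapy.
- 5.5.1 (b) and (c) (DLT at the 25% dose; slow recovery): removal from protocol therapy.
- 5.4.4.1 (other related Grade 4): withdrawal from the study.

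Section 5.5.1 does not list Grade 4 toxicity as such. For a Grade 4 event at full dose that recovers promptly, (b) and (c) do not apply and (f) is discretionary. The only specific disposition is then the sentence in 5.4.4.1, so a site could take it as deliberate.

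**2. Which endpoints are exposed, and when?**
- *Overall survival, 9.2.1:* starts at randomization, so withdrawal in any course cuts it short. Section 6.5 starts survival at the post-course-2 evaluation; under that definition only later withdrawals matter.
- *Time to recurrence:* a subject withdrawn before the post-course-2 evaluation has no time to recurrence under either reading. Section 9.3.2 allows for such subjects by accruing up to 20. Only later withdrawals, essentially in course 3, lose data.
- *Late toxicity:* 14.1.1 keeps persistent related toxicity under follow-up until it resolves or is deemed permanent. New late effects are not covered by that clause.

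**3. Size per subject.** First, the plan's own precision figure. The 90% Wilson interval is [p + z²/2n ± z√(p(1−p)/n + z²/4n²)] / (1 + z²/n), with z = 1.645. At p = 8/16 it gives 0.310 to 0.690, width 0.380, which agrees with Table 9 and the stated 38%.

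If k of 16 subjects have unknown two-year status:

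| k | Rate left undetermined (k/16) | Maximum 90% width with n = 16 − k |
|---|---|---|
| 1 | 6.25 points | 0.391 |
| 2 | 12.5 points | 0.402 |
| 3 | 18.75 points | 0.415 |
| 4 | 25 points | 0.429 |

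The interval barely widens. The damage is the undetermined part of the rate, which the interval does not show. If all 20 accrued subjects were analysed for survival, the step would be 1/20 = 5 points.

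**4. How often?** The documents give no rate of non-exempt related Grade 4 toxicity.
- Phase I (1.3.5) reports no Grade 4 toxicity in 33 subjects. The one-sided 95% upper limit is 1 − 0.05^(1/33) = 8.7%, and 16 × 0.087 = 1.4 subjects.
- Those 33 span 0.8 to 7.5 mg/m²/day. Only 6 + 6 = 12 received 6.0 or 7.5, and 0 of 12 gives 1 − 0.05^(1/12) = 22%, or about 3.5 of 16.
- The 14-subject Phase II study at 6 mg/m²/day reported no protocol-defined DLTs. If that means no Grade 4 events, which is an assumption, 0 of 47 gives 1 − 0.05^(1/47) = 6.2%, about 1 of 16.
- At assumed rates of 5%, 10% and 20%, the expected number among 16 is 0.8, 1.6 and 3.2. The chance of at least one, 1 − (1 − rate)^16, is 56%, 81% and 97%.

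**The case against.** The strongest reply is that no data need be lost. The section that defines Off Study status requires follow-up and omits toxicity as a reason to end it. The disputed phrase sits in a dose-reduction section, in contrast with continued therapy, so it can be read as loose wording for stopping treatment. This stands as far as it goes. The loss is conditional on a site letting 5.4.4.1 override 5.5.1 and 5.5.2. It does not remove the contradiction, because the documents give no order of precedence.

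A reader might infer more than the text supports in four ways.
- *That data collection does stop in the subjects with the worst toxicity.* The documents say both things; they do not settle it.
- *That most subjects with Grade 4 toxicity are affected.* The rule covers the Grade 4 categories left after the exceptions, and no count of subjects supports that claim.
- *That Section 9.4.9 shows the scale, since the any-Grade-4-DLT rule is not met at 8 of 17 (its threshold is 9 of 17).* That rule counts every Grade 4 DLT. Under 5.4.3 this includes the brief haematologic, gastrointestinal and fatigue events that 5.4.4.1 does not withdraw, so it is not a count of withdrawals.
- *That the conflict between 6.6 and 7.6 undermines objective 2.2.1.* The late-effects part of that objective is limited to subjects in remission, so toxicity follow-up after recurrence lies outside it.

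A further caution is fair. Rewriting 5.4.4.1 as removal from therapy would touch re-treatment rules that already disagree. Sections 10.2.4 and 10.2.6 allow restart after some Grade 4 events on terms that differ from 5.4.4.1.

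**Conclusion.** The contradiction is real and should be corrected; whether data are lost depends on how sites read it. Under the literal reading, overall survival as defined in 9.2.1 is informatively censored whichever course the event occurs in. Time to recurrence is affected only for withdrawals after the post-course-2 evaluation, and late-toxicity data could be lost.

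The size is 6.25 percentage points of a two-year rate per subject of unknown status, taking the plan's 16 as denominator. Phase I as a whole is compatible with up to about 1.4 such subjects in 16; the small number treated at 6.0 or above leaves room for more. These limits treat each observed zero as binomial and assume that the earlier experience carries over to three courses here. Figure 1, on dose modification, was not available in the text reviewed and could not be checked.

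**What to change.** In 5.4.4.1, delete study withdrawal as a follow-up status. State instead that, whatever the treatment decision, subjects with related Grade 4 toxicity are followed for recurrence, survival and toxicity until a 5.5.2 criterion is met. This is one sentence and adds no visits beyond those that 5.5.1 already requires.

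The change should take no position on who may be re-treated. The Grade 4 re-treatment wording in 5.4.4.1, 10.2.4 and 10.2.6 needs separate reconciliation by the sponsor.

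As a minor, separate item, 6.6 should be reconciled with 7.6 and Table 8 footnote 1 in a single statement of what toxicity data, if any, are collected after recurrence. If the sponsor settles on 6.6, this could add assessments that Table 8 does not now call for.
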